10.3.1.2.1 FOLLOW-UP FOR THE MALIGNANCY COHORT

For the primary and secondary objectives related to malignancies, follow-up will start after a 12months latency period after the index date (Figure 7). The latency period will be used to accommodate for the period between the exposure to drug and the diagnosis of cancer [72]. During this period, a malignancy diagnosis will not be considered an outcome of interest because of the low probability of being related with anifrolumab or other SOC new exposure. Additionally, a 12month at risk window after the end of the treatment episode will capture malignancies diagnosed soon after drug discontinuation to avoid possible bias caused by not being able to pinpoint the discontinuation date more accurately. Thus, follow-up ends at the end of treatment episode plus 12 months, occurrence of the first malignancy or at any of the **censoring** events (i.e., loss to followup for disenrollment/de-registering, death, or end of the study period/date of data extraction), whichever occurs first.

[figure not shown]

Figure 7 Follow-up assessment for the malignancy cohort (main analysis) Abbreviations: SLE, systemic lupus erythematosus; SOC, standard of care

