7 MILESTONES

Study milestones are summarised in Table 1.

Data collection (this refers to first data extraction) is expected to start on 31 May 2025. This start date considers the duration of time required to process all required ethics and data access applications in the countries of interest. This time may vary between approximately 7 and 18 months.

Study progress will be reported in the Periodic Safety Update Reports and will contain patient counts for the available data sources and any relevant amendments required for database applications. A preliminary assessment of the assumptions of anifrolumab uptake will be conducted to address the need of mitigation plans such as the inclusion of additional data sources or extension of the study time period.

One joint interim report (Interim report 1 SI & M) will be submitted for the *serious infections* and *malignancy* outcomes on 31 May 2027. Another interim report (Interim report 2 M) will be submitted exclusively for the *malignancy* outcome on 31 May 2030. Interim report 1 will contain descriptive analyses relevant to primary and secondary objectives, only for those data sources for which relevant data are available for reporting. The assumptions of anifrolumab uptake will be re-assessed to evaluate the feasibility of the final study report milestones. If the assumptions do not hold, mitigation steps will be explored.

The second interim report is related to *malignancy outcomes* and will be submitted 36 months after the first interim report. It will contain descriptive analyses relevant to primary and secondary objectives, only for those data sources for which relevant data are available for the reporting.

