10.2.1 Study time periods

The study time period for analysis will be based on availability of information from the data sources and on the date of market availability for anifrolumab. The **start of the study period** will be the market launch date of anifrolumab in each country (Table 3); this considers that all data sources included in the study are available for at least 12 months before that date (12 months correspond to the minimum look-back period before index date for confounders and/or risk factors).

The **end of study period**, defined as the last possible day of follow-up when all patients still in the study are censored, will likely differ between countries and will depend on length of data lag in each country at the time when the last data extraction is performed (Table 3). The rationale for this choice is to include all data available from relevant data sources to capture a sufficient number of outcomes and exposures for the primary outcomes at study.

Country	Start of study	Start of	End of	End of	End of study	End of study
	period ^a	enrolment ^b	enrolment for	enrolment	period for SI	period for M
		Date when first	SI outcomes ^c	for M	outcomes ^e	outcomes ^f
		patient can be	Date when last	outcomes ^d	Last possible	Last possible
		enrolled	patient can be	Date of last	day of	day of follow-
			enrolled	patient	follow-up,	up, when all
				enrolled	when all	patients still
					patients still	active are
					included are	censored
					censored	
Denmark	04 May 2022	04 May 2022	30 April 2025	31 May 2028	31 May 2025	31 May 2029
France	19 April 2022	19 April 2022	30 April 2025	31 May 2028	31 May 2025	31 May 2029
Germany	11 March 2022	11 March 2022	30 April 2025	31 May 2028	31 May 2025	31 May 2029
Spain	May 2023 (Tbc)	May 2023 (Tbc)	30 April 2025	31 May 2028	31 May 2025	31 May 2029

Table 3 Relevant dates of the study by country

Abbreviations: SI, serious infection; M, malignancy; Tbc, to be confirmed.

^aAnifrolumab market launch date.

^bStart of enrolment is same for the serious infections and malignancy cohorts.

°For infections the last patient will be included 1 month before the end of study period.

^dFor malignancies the last patient will be included 12 months before the end of study period.

^eCalculated assuming that the final report is due on 30 Nov 2028, assuming a two-year lag time in data availability. Needs to be adapted by country after feasibility study.

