^fCalculated assuming that the final report is due on 30 Nov 2032, assuming a two-year lag time in data availability. Needs to be adapted by country after feasibility study.

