The Danish Cancer Register contains patient-level data on incident cancers in the Danish population. Data must be reported to the register according to an executive order by The National Board of Health. Data are available from 1943 and onwards, however, reporting was voluntary until March 1987. The register contains information on date of diagnosis, location, classification of malignant tumours (TNM ["Tumour", "Node", and "Metastasis" categories] - a classification system to describe the amount and spread of malignant tumours in a patient's body), and histological classification of cancer. Information from the NPR, the Cause of Death Register, and the Danish Pathology Register is used to increase completion and accuracy of data collection in the process of updating the Cancer Registry. Validation of the Cancer Register and selected clinical cancer databases was reported in 2012 by the authorities with histological verification of 92-96% of the tumours, and even close to 100% in some cancer types, including melanoma, breast, lung, and colon cancer.

The register is updated once a year after December with a lag of approximately 13 months. Since 2004, the 3rd edition of the international classification of diseases for oncology (ICD-O-3) has been used as the classification system. The ICD-7 classification was used until 1977. Between 1978 and 2003, ICD-O-1 was used.

• Danish Cause of Death Register

The Danish Cause of Death Register (CDR) contains information on date and cause of death. The information from the death certificate, including place of death, information about any autopsy, and municipality of residence is transferred to the Cause of Death register. Date of death is available from 1970 and onwards. The register is updated once a year after December with a lag of approximately 13 months.

• The National Health Insurance Service Register

The National Health Insurance service register (*Sygesikringsregisteret* [NHISR]) contains information on services supported by public health insurance and provided by general practitioners (GPs) and specialists in private practice outside the secondary setting at hospitals. Information on the weekly invoicing of the costs covered by the public health insurance is included in the register.

However, individual diagnoses and treatment information are not available. Data are available from 1990 and onwards.

• Socio-economic registers at Statistics Denmark

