Similarly, information on a conducted diagnostic test is only available if being subject to reimbursement. Test results are not available from the claims data. Sociodemographic information is partially available. However, data on lifestyle factors are not recorded.

SHI data in Germany are updated yearly. The estimated lag time (from the time data are recorded until available for research) is currently 15-16 months or more. At the time of feasibility assessment (June 2022) data for the period between January 2011 up to December 2020 were available; data from 2022 will be available in 2024.

Study-specific data

In Germany, market launch for anifrolumab occurred in March 2022 (Table 3). Anifrolumab is expected to be captured, since belimumab data are available through prescription or dispensation. Administration during hospital stay is not captured.

Data on SLE SOC exposure is considered available for most drugs since 2011, except for mepacrine which is no longer available in Germany. Data on prescribed outpatient therapy are available. Data on biologics are available through prescription data on German national drug code unique identifier (*Pharmazentralnummer* [PZN]) level and some OPS inpatient codes.

Data on malignancies (overall and sub-types) and serious infections (overall and sub-types) are available for inpatients and outpatients if coded trough ICD-10 GM. Date of death is available. Intravenous antimicrobials can be captured from the prescriptions and dispensations in outpatient visits.

Data on covariates are generally available (Table 26), except for vaccination (substance not captured), BMI (including weight or height), alcohol consumption and smoking. Procedures with radiation exposure may be available if procedure codes are registered.

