Sample size and representativeness

• The inclusion of several countries contributes to the sample size and representativeness of European anifrolumab users. However, SLE clinical management may occur in healthcare settings that are not part of some of the data sources (e.g., private care) which could result in the exclusion of potential eligible patients. Possible selection bias may occur if patients in the other settings are different from those included in terms of outcome risk. However, in the included countries, anifrolumab is more likely to be available in secondary care (hospitals or SLE specialised clinics) which would minimise selection bias.

• SLE is not a very common disease. The selection of patients with moderate to severe uncontrolled disease and matching with a comparator cohort with a similar SOC duration may increase internal validity. However, it is possible that some anifrolumab exposed patients who do not have suitably matched comparators may have to be excluded from the study. Despite this exclusion, it is assumed that these patients may be too different from the general moderate/severe SLE patient population in the real-world setting.

Data sources and data availability (overall)

• Automated healthcare databases are appropriate for real-world studies because of the recording of prescription and clinical data in the absence of a specific research question. However, the accuracy of the analyses to answer any given research question depends to some degree on the accuracy of the available information. Data collected for administrative purposes may have incomplete medical information which is not directly related to reimbursement (e.g., body mass index). This can affect the measurement of variables that may be important covariates for the assessment of the association between anifrolumab use and the occurrence of serious infections and malignancies. To minimise the risk of including incomplete information, all retrieved data will be reviewed for possible inconsistences or implausible information.

• Some data sources have relatively long lag times. Denmark, France and Germany have particularly long lag periods (up to 13 months in Denmark and 12 months in France and Germany), which could limit availability of data. However, an assumption of a data lag time of approximately 2 years will be implemented to maximise capturing available data.

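### As worded, the censoring rule ignores data lag at interim extractions, so the interim malignancy incidence rates would count person-time in which no event can yet be seen

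*Protocol*

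**What the plan says.** For malignancy, section 10.3.1.2.1 starts follow-up 12 months after the index date and runs it to 12 months after the end of the treatment episode, the first malignancy, or a censoring event. The censoring list ends with "death, or end of the study period/date of data extraction), whichever occurs first". Section 10.3.1.2.2 uses the same words for serious infections, without the extra 12 months, and Table 2 footnote c repeats the rule.

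An anifrolumab episode (section 10.3.1.2) closes 30 days plus 16 weeks after the last registered dose. Section 10.7.1.3 divides events by total person-years at risk.

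On lag, section 10.2.1 says "The study time period for analysis will be based on availability of information from the data sources". It adds that the country end date will "depend on length of data lag in each country at the time when the last data extraction is performed". The Table 3 footnotes derive both end dates from the final-report dates, "assuming a two-year lag time in data availability". Section 10.9 says "an assumption of a data lag time of approximately 2 years will be implemented".

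The stated source lags are:
- Spain: about 6 months (section 10.4.1.4).
- France: 12 months (Table 7).
- Danish Cancer Register: "The register is updated once a year after December with a lag of approximately 13 months" (section 10.4.1.1).
- Germany: "The estimated lag time (from the time data are recorded until available for research) is currently 15-16 months or more" (section 10.4.1.3), but 12 months in Table 7 and section 10.9.

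Section 7 says "Interim report 1 will contain descriptive analyses relevant to primary and secondary objectives", limited to data sources with relevant data available, and describes interim report 2 in the same way. Table 2 classes the primary incidence objectives (1 and 3) as descriptive.

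**The concern.** At any extraction, events and prescriptions are visible only up to a data-complete date, which is roughly the extraction date minus the lag. A patient still on treatment at that date does not stop contributing time there. The clearance period and, for malignancy, the 12-month off-drug window carry follow-up forward until the extraction date or the study end date stops it. Those months add to the denominator and cannot add to the numerator.

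The interim reports contain no hazard ratios, so these rates are the main quantitative malignancy evidence the regulator receives before the final malignancy report of 30 November 2032. In a safety study, a rate that is too low reassures falsely.

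**Working it through.** **Inputs.** Yearly anifrolumab initiators by country come from Table 27, launch and end dates from Table 3, report dates from Table 1, and lags from section 10.4. As a check on the base, 183 + 2,695 + 216 + 412 = 3,506, which agrees with Table 8. The infection cohort sums to 89 + 1,005 + 126 + 216 = 1,436, against 1,435 stated. The protocol gives no interim rate, interim person-years or interim extraction date to reproduce.

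**Step 1: where the dates already protect the analysis.**
- Study end to final report: 31 May 2025 to 30 November 2028 (infections) and 31 May 2029 to 30 November 2032 (malignancy). Both are 42 months, longer than any stated lag.
- Infection study end to interim 1: 31 May 2025 to 31 May 2027 = 24 months, also longer than any stated lag.
- Malignancy at interim 1: the study end of 31 May 2029 is still in the future, so the extraction date is the only administrative limit.
- Malignancy study end to interim 2: 31 May 2029 to 31 May 2030 = 12 months. This equals the French lag and is shorter than the Danish Cancer Register lag and the longer German figure.

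**Step 2: length of the tail.** Infections: 30 + 112 = 142 days = 4.7 months. Malignancy: 142 + 365 = 507 days = 16.7 months, enough to span every lag above.

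By hand, take a French patient who started 36 months before a malignancy extraction and is still treated. The data-complete date is month 24. Visible at-risk time is month 12 to 24, or 12 months. Counted time is month 12 to 36, or 24 months. The rate is halved.

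**Step 3: cohort calculation (anifrolumab arm).** Let D = extraction date − lag.
- Counted end = min(last visible dose + tail, extraction date, study end).
- Visible end = min(counted end, D).
- Ratio = total visible person-time / total counted person-time, and observed rate = true rate × ratio.

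Assumptions: initiations are spread evenly within each year; table entries below 10 are set to 5; Spain starts mid-May 2023; patients enter only if initiation is visible by D; a persisting patient's last visible dose is placed at D; discontinuation is 0-15% per year. Lags in months are Denmark 13, France 12, Germany 12 to 16, Spain 6.

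| Outcome | Assumed extraction | Ratio | Understatement |
|---|---|---|---|
| Malignancy, interim 1 | 31 May 2026 | 0.35-0.38 | 62-65% |
| Malignancy, interim 1 | 30 Nov 2026 | 0.42-0.45 | 55-58% |
| Malignancy, interim 2 | 30 Nov 2029 | 0.82-0.84 | 16-18% |
| Malignancy, interim 2 | 31 May 2030 | 0.99-1.00 | 0-1% |
| Infections, interim 1 | 31 May 2026 | 0.97-1.00 | 0-3% |
| Infections, interim 1 | 30 Nov 2026 | 1.00 | 0% |

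Worked case (30 November 2026, Germany 15 months, full persistence), visible/counted person-years: Denmark 65/141, France 460/1,195, Germany 70/186, Spain 163/256. The total is 758/1,779 (unrounded sum) = 0.426. A true rate of 6.31 per 1,000 person-years, the SLE figure in section 10.5.2, would read 6.31 × 0.426 = 2.7. For interim 2 on 30 November 2029 the same lags give 6,396/7,821 = 0.818, and 6.31 would read 5.2.

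**Step 4: sensitivity to the disputed lags.** Under full persistence, the shortest figures (Denmark 2, Germany 12) give 53% at 30 November 2026. The longest (Denmark 15, Germany 16) give 65% at 31 May 2026, 19% at 30 November 2029, and 4% for infections at 31 May 2026.

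**The case against.** The strongest reply is that the protocol plainly knows about lag. Section 10.2.1 bases the analysis period on data availability and lets the end date vary by country. Section 10.9 adopts a lag of about two years without confining it to the final reports. Section 7 limits the interims to data sources with relevant data. On this view the slash in the censoring rule is shorthand, and the data-complete date is a derivation that section 10.7 leaves to the SAP.

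Part of this stands. The understatement is a consequence of the wording, not a stated intention, and a careful analyst might avoid it. A reader might infer that the protocol ignores lag altogether; it does not.

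The reply does not cure the interim gap. The lag-dependent end date is set at the last extraction, and the two-year allowance in Table 3 is counted back from the final reports. Choosing which sources to report does not say where a patient's follow-up stops. Nor is this only detail left to the SAP: the protocol states a rule, and the rule gives the wrong date. Under section 10.6 the German and Spanish data are analysed by their own providers, so several teams must read it identically.

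**Conclusion.** The point holds for the interim malignancy incidence rates. Taken as written, the rule would understate them by about 55-65% at interim 1 for an extraction between May and November 2026. At interim 2 the figure is about 16-18% for a November 2029 extraction, falling to 0-1% for one in May 2030. These sizes rest on assumed extraction dates, the Table 27 uptake forecast and 0-15% yearly discontinuation.

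Three stronger readings are not supported:
- **All interim rates are badly wrong.** Infection rates move by about 0-3%. A loss of about one third arises only if interim 1 used data from the first extraction on 31 May 2025. The protocol gives that as the day extraction starts, two years before the report, and nowhere as the interim cut-off. Malignancy losses near 87% need the same early cut.
- **Anifrolumab is made to look safer than standard of care.** That needs a shorter tail for the comparator drugs. The protocol makes their clearance windows drug-specific, gives no lengths, and continues the episode across switches and add-ons. The 12-month malignancy window applies to both arms.
- **The final results are biased.** The 42-month gap protects the final rates, hazard ratios and meta-analyses.

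**What to change.** In Table 2 footnote c and sections 10.3.1.2.1 and 10.3.1.2.2, replace the extraction date with the last date on which all sources needed for that outcome (drug, hospital, cancer and death records, as applicable) are complete in that data source for the extraction in question. Say that this applies to every interim and final analysis, and that the clearance period and the 12-month off-drug window are truncated there.

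Reconcile the lag figures: Germany is 12 months in Table 7 and section 10.9 but 15-16 or more in section 10.4.1.3. Denmark is 2-13 in Table 7, about 2 (health registers), 3-15 (linked data) and 13 (Cancer Register) in section 10.4.1.1, and up to 13 in section 10.9.

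The cost is a sentence of text and less interim person-time, hence wider interim confidence intervals. No new data are needed.

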10.3.1.2.2 FOLLOW-UP FOR THE SERIOUS INFECTION COHORT

For the serious infection primary and secondary objectives, follow-up starts at index date and ends at the end of the treatment episode (Figure 8), occurrence of a serious infection or at any of the **censoring** events (loss to follow-up for disenrollment/de-registering, death, or end of the study period/date of data extraction), whichever occurs first.

For the exploratory objective, follow-up ends at the end of treatment episode or any of the censoring events: loss to follow-up for disenrollment/de-registering, death, or end of the study period/date of data extraction, whichever occurs first.

Figure 8 Follow-up assessment for the serious infection cohort (main analysis) Abbreviations: SLE, systemic lupus erythematosus; SOC, standard of care

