- 9) To estimate the incidence of the first occurrence of opportunistic serious infections, other serious infections, pneumonia (overall), fatal and non-fatal pneumonia (separately) in moderate/severe SLE patients initiating anifrolumab and in comparable moderate/severe SLE patients who do not initiate anifrolumab (exposed to SLE SOC).
- 10) To compare hazard rates of the first occurrence of opportunistic serious infections, other serious infections, pneumonia (overall), fatal and non-fatal pneumonia (separately) in moderate/severe SLE patients initiating anifrolumab versus comparable moderate/severe SLE patients who do not initiate anifrolumab (exposed to SLE SOC), when feasible (i.e., if sample size allows).

Exploratory objectives

The following objectives pertain to the serious infection outcomes:

- 11) To estimate the incidence of recurrent infections leading to hospitalisation, in moderate/severe SLE patients initiating anifrolumab and in comparable moderate/severe SLE patients who do not initiate anifrolumab (exposed to SLE SOC).
- 12) To compare the hazard rates of recurrent infections leading to hospitalisation in moderate/severe SLE patients initiating anifrolumab and in comparable moderate/severe SLE patients who do not initiate anifrolumab (exposed to SLE SOC), when feasible.

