Two cohorts will be constructed for each of the outcomes of interest: new malignancies (composite and separately by malignancies sub-types) and serious infections for serious infections outcomes), considering outcome-specific inclusion and exclusion criteria (Figure 2 and Figure 3). This approach maximises sample size and overcomes cessation of follow-up due to occurrence of multiple events. Patients may be included in multiple cohorts.

[figure not shown]

Figure 1 Time-based exposure sets for the potential eligible comparators

Abbreviations: SLE, systemic lupus erythematosus; SOC, standard of care

Note: The figure presents time since the first SLE SOC (not calendar time). Patient 1 represents one patient that initiated aniforlumab; patients 2 and 4 are potential comparators for patient 1, considering SLE SOC around aniforlumab initiation for patient 1 and the same duration of SLE SOC until aniforlumab initiation.

[figure not shown]

Figure 2 Overview of study design for malignancies

^a Date of the first anifrolumab prescription (and corresponding date for SLE SOC patients).

^b Uncontrolled SLE: ≥ 1 flare.

^cCensoring criteria will be the earliest of: malignancy diagnosis; end of treatment episode; loss to follow-up (disenrollment/de-registering); death; end of study period.

Abbreviations: SLE, systemic lupus erythematosus; SOC, standard of care

[figure not shown]

Figure 3 Overview of study design for serious infections

^a Date of the first anifrolumab prescription (and corresponding date for SLE SOC patients).

^b Uncontrolled SLE: ≥ 1 flare.

^cCensoring criteria will be the earliest of: serious infection diagnosis; end of treatment episode; loss to follow-up (disenrollment/de-registering); death; end of study period. For the analysis of recurrent infections (exploratory objectives 11 and 12), serious infection diagnosis will not be considered as censoring variable. Abbreviations: SLE, systemic lupus erythematosus; SOC, standard of care

robieviations. SEE, systemic rupus erythematosus, soe, standard of care

The summary of study design for each objective is presented in Table 2.

Obj	Description	Population ^a	Follow up	Follow-up Outcome		Analysis		Analysis
3	-	ropulation	ronow-up	Ошеоше	D	С	MA	stratification
Prima	ry objectives		1	1		-		

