8	Describe the frequency of each component of serious infection definition	 Adult patients Moderate to severe SLE Uncontrolled SLE Exposure to SOC or anifrolumab No prior malignancy diagnosis No prior HIV/AIDS or congenital immunodeficiency diagnosis No prior transplant No prior serious infection (6 months) Matching on: SOC duration, PS 	NA: At the first serious infection	 First serious infection component (separately): Infection leading to hospitalisation Use of IV antimicrobials Infection-related death 	x			Treatment group (exposed and unexposed to anifrolumab)
9	Estimate the incidence of opportunistic serious infections, other serious infections, pneumonia (overall, fatal and non-fatal) (separately)	 Adult patients Moderate to severe SLE Uncontrolled SLE Exposure to SOC or anifrolumab No prior malignancy diagnosis No prior HIV/AIDS or congenital immunodeficiency diagnosis No prior transplant No prior serious infection (6 months) Matching on: SOC duration, PS 	Index date until: - End of treatment episode - Occurrence of the first serious infection - Other censoring criteria ^c	 First serious infection sub- type (separately): Opportunistic serious infection Other serious infections Pneumonia (overall) Fatal pneumonia Non-fatal pneumonia 	X			Treatment group (exposed and unexposed to anifrolumab)
10	Compare the incidence of opportunistic serious infections, other serious infections, pneumonia (overall, fatal and non-fatal) (separately) by treatment group	 Adult patients Moderate to severe SLE Uncontrolled SLE Exposure to SOC or anifrolumab No prior malignancy diagnosis No prior HIV/AIDS or congenital immunodeficiency diagnosis No prior transplant No prior serious infection (6 months) Matching on: SOC duration, PS 	Index date until: - End of treatment episode - Occurrence of the first serious infection - Other censoring criteria ^c	 First serious infection sub- type (separately): Opportunistic serious infection Other serious infections Pneumonia (overall) Fatal pneumonia Non-fatal pneumonia 		X		NA
Explo	ratory objectives				 	 		
11	Describe the incidence of recurrent infections leading to hospitalisation	- Adult patients - Moderate to severe SLE - Uncontrolled SLE - Exposure to SOC or anifrolumab	Index date until: - End of treatment episode - Other censoring criteria ^c	 All infections leading to hospitalisation 	х			Treatment group (exposed and unexposed to anifrolumab)

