The first serious infection after index date will be included. Date of each serious infection episode will be the date of infection leading to hospitalisation, use of IV antimicrobials or death, whichever occurs first. The frequency of each serious infection component – infection leading to hospitalisation, requiring treatment with IV antimicrobials and infection-related deaths – will be described as a **secondary** objective (secondary objective 8) and comparative analyses on each component will be conducted as sensitivity analysis, where possible (Section 10.7.1.7).

As **secondary outcomes**, opportunistic serious infections, other serious infections, pneumonia (overall, fatal and non-fatal) will be analysed separately (objectives 9 and $10)^6$. Additionally, the proportion of serious infections due to COVID-19 infection will be described for patients exposed and unexposed to anifrolumab.

The definition of opportunistic infections may be challenging. To define opportunistic infections detailed clinical information is often needed and, at some level almost all agents could be considered opportunistic in that they are typically more likely to occur, or present more severely in immunosuppressed patients [99]. Therefore, classifying infections as opportunistic using secondary data is challenging. In recognition of this challenge, efforts have been made by a consensus committee (which included infectious disease, public health, and pulmonary physicians with subject matter expertise in mycobacterial, fungal, viral, bacterial or parasitic infections, as well as rheumatology physicians) to harmonize a list of infections that could be considered as opportunistic for use in clinical trials and observational studies involving biologics and other disease modifying antirheumatic drugs. The consensus list of infections was based on a systematic review of several observational studies, clinical trials, case series, and expert opinion by the committee [99].

In this study, opportunistic infections are defined based on the list of infections provided by the consensus committee with two considerations: all infections that could be mapped to ICD-10 codes

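### Objectives 9 and 10 ask for the first occurrence of each infection sub-type, but follow-up stops at the first serious infection of any kind, so a narrower quantity is estimated

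*Protocol*

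**What the plan says.** **Targets.** Protocol Section 9.1, objective 9: "To estimate the incidence of the first occurrence of opportunistic serious infections, other serious infections, pneumonia (overall), fatal and non-fatal pneumonia (separately". Objective 10 is the comparison: "To compare hazard rates of the first occurrence of opportunistic serious infections, other serious infections, pneumonia (overall), fatal and non-fatal pneumonia (separately". Both name first occurrence of the sub-type.

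**Follow-up rule.** Section 10.3.1.2.2 covers the primary and secondary infection objectives together; follow-up "ends at the end of the treatment episode (Figure 8), occurrence of a serious infection", or at a censoring event. Table 2 (Section 10.1) gives for objectives 9 and 10: "Index date until: - End of treatment episode - Occurrence of the first serious infection - Other censoring criteria". The Figure 3 footnote also stops at a serious infection diagnosis, and it lifts the stop only for the recurrent-infection objectives 11 and 12, where "serious infection diagnosis will not be considered as censoring variable".

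**Events counted.** Section 10.3.2.2: "The first serious infection after index date will be included".

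**Text leaning the other way.** Section 10.3.2.2 describes pneumonia as a composite of all cases identified. Section 10.7.1.3 says that only the event under study is considered, but its example is infection versus malignancy, not one infection sub-type versus another. Neither sentence exempts objectives 9 and 10 from the stop.

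**The concern.** Take a patient admitted with a urinary tract infection who, still on treatment, later develops an opportunistic infection or a fatal pneumonia. That is a first occurrence of the sub-type as objectives 9 and 10 define their target, yet it falls after follow-up has closed. Section 10.3.3.2 states that previous infection raises the risk of a further one, so the rule closes follow-up in patients whom the protocol itself regards as at higher risk. Section 10.1 justifies separate outcome cohorts partly as a way to avoid ending follow-up because of other events; among infection sub-types the rule brings that back.

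At stake are the sub-type rates and hazard ratios. Any loss grows with the overall infection rate, so it would be larger in the anifrolumab arm if the drug raises that rate. The sub-types may be rare, and objective 10 is already conditional on sample size.

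**Working it through.** **Plan's own figure.** Section 10.5.2 sizes only the composite (1,312 exposed patients for 80% power). No size is stated for the sub-types. Re-simulating the composite with the protocol's inputs (Table 13 shares, HR 1.5, SD 0.2, 1:3, 39.8 per 1,000 person-years, 2 years, random-effects pooling) gave power 0.796 at 1,312, so the inputs are read as the plan uses them.

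**Inputs from Section 10.5.2.** Comparator rate λ = 0.0398 per year; exposed rate at HR 1.5, λ = 0.0597; T = 2 years.

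**Assumed, not in the documents.** Sub-type share of serious infections s = 5%, 10%, 30%, equal in both arms; risk multiplier after a first infection m = 1, 3, 5; constant rates; follow-up running to T.

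**Step 1: patients who leave follow-up for every sub-type.** 1 − exp(−λT): comparators 1 − exp(−0.0796) = 7.7%; exposed 1 − exp(−0.1194) = 11.3%.

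**Step 2: events.**
- Counted (sub-type is the first serious infection): A = s(1 − exp(−λT)).
- Lost (first sub-type event after another serious infection): B = ∫₀ᵀ (1−s)λ exp(−λt)[1 − exp(−msλ(T−t))] dt.
- Share lost = B/(A+B). Approximately B/A ≈ (1−s)mλT/2, so the loss shrinks roughly in proportion if follow-up is shorter.

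Comparators, s = 10%, per 1,000 patients: A = 7.651; B = 0.277, 0.826, 1.370 for m = 1, 3, 5. Shares: 0.277/7.928 = 3.5%; 0.826/8.477 = 9.7%; 1.370/9.021 = 15.2%.

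**Step 3: person-time rates.** The stop removes person-time as well as events.
- Under the plan's rule: PT₁ = (1 − exp(−λT))/λ, and the rate is A/PT₁ = sλ.
- With follow-up to the sub-type's own first event: add PT₂ = B/(msλ); the rate is (A+B)/(PT₁+PT₂).

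Same example, PT₁ = 1,922.5 years and plan rate 3.98 per 1,000:
- m = 1: PT₂ = 69.6; rate 7.928/1,992.1 = 3.98. No difference.
- m = 3: PT₂ = 69.2; rate 8.477/1,991.7 = 4.26. The plan's rate is 6.5% too low.
- m = 5: PT₂ = 68.9; rate 9.021/1,991.3 = 4.53. The plan's rate is 12% too low.

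**Step 4: ranges over s = 5-30%.** The last column is the exposed/comparator rate ratio, used as an approximation to the HR; under the plan's rule it is 1.50 throughout.

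| m | Events lost, comparator | Events lost, 1.5-fold arm | Rate too low, comparator | Rate too low, 1.5-fold arm | Ratio with full follow-up |
|---|---|---|---|---|---|
| 1 | 2.7-3.7% | 4.0-5.5% | 0 | 0 | 1.50 |
| 3 | 7.6-10.3% | 11.0-14.7% | 5.1-6.8% | 7.3-9.8% | 1.54-1.55 |
| 5 | 11.9-16.0% | 16.7-22.3% | 9.6-12.8% | 13.4-17.8% | 1.57-1.59 |

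**Step 5: in events.** With 1,312 exposed patients, HR 1.5 and s = 5%, 1,312 × 0.05 × 0.1125 = 7.4 exposed sub-type events are counted. Lost per 1,000 exposed: 0.325, 0.971, 1.611 for m = 1, 3, 5; times 1.312 gives 0.4, 1.3 and 2.1 events.

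**Sensitivity.** The 39.8 rate comes from a study that counted only hospitalisations with infection as primary diagnosis; this protocol's composite is wider. If the composite ran at 100-150 per 1,000 person-years (assumed), the loss would be 6.6-13.0% at m = 1 and 24.7-42.2% at m = 5.

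**The case against.** The strongest defence is that this is a coherent design. Censoring at another first serious infection gives the cause-specific rate and hazard of the sub-type as first serious infection, which is standard and interpretable. Table 2's outcome column for objectives 9 and 10 speaks of the first serious infection sub-type, and Section 10.3.2.1 builds malignancy sub-types in the same way, as types of the first malignancy. This stands as far as it goes: a reader might infer that objectives 9 and 10 go unanswered, and the documents do not support that. But for malignancy the restriction is written out; for infections the objectives ask for something wider, and the mismatch remains.

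A reader might also infer that later infections are never counted. Those leading to hospitalisation do enter objectives 11 and 12, though not by sub-type. Nor does the rule always pull the HR toward 1: with unchanged risk after infection, rate and HR are unbiased and only precision suffers. The 3- to 5-fold multipliers are assumptions; the protocol gives a direction but no size.

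Finally, the remedy is not neutral. Follow-up is on-treatment, and the protocol expects infections to be among the main reasons for stopping anifrolumab (Section 10.3.1.2, footnote 4), while it expects few patients to be without any standard of care (Section 10.9). Time after a first infection may then be cut short more in the exposed arm, which also reduces the events that can be recovered there. This is a limitation to report, not a reason to discard rare safety events.

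**Conclusion.** The conflict is real and lies within the protocol: the stated target is the first occurrence of each sub-type, and the stated follow-up delivers the sub-type only when it is the first serious infection. The size is modest at the protocol's own rate. Most sub-type events are still counted under every scenario in the main table, and whether there is bias, as opposed to lost precision, depends on risk rising after a first infection. Where it does rise, the attenuation runs in the unfavourable direction for a safety study, hiding a small part of an excess. The figures rest on the assumed sub-type shares and multipliers, constant rates, and a full 2 years of follow-up. The primary objectives 3 and 4 are not affected. The change is worth making because it is cheap and the events concerned are few.

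**What to change.** For objectives 9 and 10, end follow-up at the first event of the sub-type under study, end of treatment episode or censoring, whichever comes first. Amend Section 10.3.1.2.2, the two rows of Table 2 and the Figure 3 footnote. Reconcile Section 10.3.2.2 (inclusion of the first serious infection only, against all identified pneumonia cases) and Section 10.7.1.3 (event under study). Keep the any-first-infection rule for objectives 3 and 4. Optionally report the sub-type as first serious infection as a supplementary analysis.

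The cost is protocol wording and one extra derivation per sub-type; objectives 11 and 12 already need follow-up past the first infection. Add to Section 10.9 that follow-up after a first infection may be cut short unequally between arms if infection leads to stopping anifrolumab.
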